#### 8.1.3 Primary and secondary endpoints

##### 8.1.3.1 Primary endpoints

###### Performance

- Level of Agreement between measurements made using GAT, Pascal DCT and the ARGOS-SC system from V09 (month 12) throughout V13 (month 36).

 Implantdata Ophthalmic Products GmbH	Clinical Investigation Plan ARGOS-SC01_Follow-up	Revision C  Page 54 of 97
---	---	---------------------------------

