## SYNOPSIS

Title	Follow-up of the first in man, prospective, open-label, single arm, multicenter clinical investigation to assess the long-term safety and performance of the ARGOS-SC suprachoroidal pressure sensor system in patients with glaucoma underwent non-penetrating glaucoma surgery (Follow-up Month 12 – Month 36)
Study Number	ARGOS-SC01_Follow-up
Sponsor	Implantata Ophthalmic Products GmbH
Name of IMD	
ARGOS-SC System
 
The ARGOS-SC system is a non-CE marked investigational medical device composed of the implant and its accessories:
 
Implant: ARGOS-SC pressure sensor implant for suprachoroidal placement
 
Accessories: MESOGRAPH reading device, telemetric Multiline Connector

Intended use	The sensor device is intended to be permanently implanted in the human eye and used in conjunction with the hand-held MESOGRAPH reading device to telemetrically measure the intraocular pressure (IOP) of the implanted eye.
Patient Population	Subjects of the ARGOS-SC01 clinical trial with an implanted ARGOS-SC pressure sensor.
Study Purpose	The purpose of this study is to evaluate the long-term safety and performance of the ARGOS-SC system.
Study Design	This study is designed as a prospective, open-label, multicenter, single-arm clinical investigation. Subjects will be followed up at regular intervals for 2 years (Month 12 – Month 36) after the ARGOS-SC implantation to collect safety and performance information.
Study Objectives	
Primary Objective
 
Performance
 
To evaluate the limits of agreement between measurements with Goldmann Applanation Tonometry (GAT), Pascal Dynamic Contour Tonometry (DCT, if available) and the ARGOS-SC system from month 12 throughout month 36 following implantation

 Implantata Ophthalmic Products GmbH	Clinical Investigation Plan ARGOS-SC01_Follow-up	Revision C  Page 7 of 97
--	---	--------------------------------

	
Secondary Objectives
 
Safety
 
To evaluate the safety and tolerability the ARGOS-SC pressure sensor throughout a follow-up period from month 12 throughout month 36.
 
Performance
 
To evaluate the performance of the ARGOS-SC system from month 12 throughout month 36 after implantation.

--	---

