### **8.2.2 Justification of the choice of comparator**

GAT, considered by the medical community to be the gold standard method of IOP measurement, will be used as comparator. However, GAT actually estimates IOP based on a measurement of the force needed to applanate a predetermined area of the cornea while the ARGOS-SC sensor will be in direct contact with the aqueous humor and measure IOP directly. Consequently, differences are anticipated between the IOP values obtained with the two devices. However, trends in IOP are expected to remain the same regardless of the method used. Therefore, to assess the accuracy of the ARGOS-SC system, IOP profiles obtained with ARGOS will be compared to those obtained with GAT.

Pascal DCT is designed to eliminate some of the measurement errors in GAT that come from variations in corneal thickness and rigidity. It is believed to be closer to true IOP, especially at higher IOPs. It is also less prone to “user error”.

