### **IOP measurement in the clinic**

IOP measurement will be conducted as a series of 2x GAT (in case of a difference of more than 2mmHg, a third GAT-measurement is required) followed by 3x ARGOS-SC system. When series of measurements are made, GAT must always be used first to avoid potential operator bias. For the ARGOS-SC measurements the patient has to stay in the same position as for the GAT-measurements (chin on chin rest, forehead installed).

Additionally (if available), a series of 2x DCT (in case of a difference of more than 2mmHg, a third DCT-measurement is required) followed by 3x ARGOS-SC will be performed after the series of GAT and ARGOS-SC measurements. For the ARGOS-SC measurements, the patient has to stay in the same position as for the DCT-measurements (chin on chin rest, forehead installed).

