#### **9.1.4 Performance Analysis**

The probability distribution of the difference of the paired measurements grouped within 1 mmHg will be compared to the primary objective of the accepted 65% of the measurements to agree between +/- 5 mmHg for > 60 measurement pairs.

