8.5 Primary endpoint

8.5.1 Performance

Level of agreement between measurements made using GAT, Pascal DCT and ARGOS-SC system at visit V09 - V13.

The primary outcome measures of the study eye are:

- Average of 2 – 3 measurements using GAT system at visit V09 – V13
- Average of 2 – 3 measurements using ARGOS-SC system at visit V09 – V13 roughly contemporaneous with the GAT measurements

Descriptive statistics for the GAT and ARGOS-SC measures per visit.

Descriptive statistics for the absolute difference between ARGOS-SC and GAT measures per visit.

The absolute difference between the ARGOS-SC and GAT measures will be scaled in $\leq 5\text{mmHg}$ and $> 5\text{ mmHg}$ and the frequency distribution will be displayed.

The concordance of the intraindividual measurement values of GAT and ARGOS-SC will be indicated by the concordance correlation coefficient r_{ccc} (→ see section 11.1), separate for each visit.

The Bland-Altman (mean-difference) plot and a X-Y -plot (Scatter-Plot) should illustrate the comparison of the two methods (→ see section 11.2).

The level of agreement between Pascal DCT and ARGOS-SC will be evaluated analogously.

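### One 65% agreement criterion covers a primary endpoint with two reference tonometers, and neither protocol nor SAP says which one decides

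*Protocol*

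**What the plan says.** Protocol 8.1.3.1 defines the primary endpoint as "Level of Agreement between measurements made using GAT, Pascal DCT and the ARGOS-SC system" over V09 to V13. The objectives (synopsis and 7.1.1) and SAP 4.1.1 and 4.2.1 also name both tonometers.

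The only criterion is in protocol 9.1.4, repeated in the synopsis: "The probability distribution of the difference of the paired measurements grouped within 1 mmHg will be compared to the primary objective", namely the "accepted 65% of the measurements to agree between +/- 5 mmHg for > 60 measurement pairs". No reference is named. A footnote says the objective will be adjusted if that many pairs are not reached, but gives no rule.

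On the standing of the two references:
- Protocol 8.2.2: "GAT, considered by the medical community to be the gold standard method of IOP measurement, will be used as comparator". The next paragraph says DCT is believed to be closer to true IOP.
- Protocol 8.3.12.13: GAT is done at every visit. DCT is conditional: "Additionally (if available), a series of 2x DCT" follows the GAT series.
- SAP 8.5.1 lists only the GAT and ARGOS-SC averages as primary outcome measures. Under the same primary-endpoint heading it adds: "The level of agreement between Pascal DCT and ARGOS-SC will be evaluated analogously".

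SAP 8.5.1 and mock-up Table 2.1.1 classify the absolute difference as up to 5 or above 5 mmHg, visit by visit. The SAP contains neither the 65% nor a decision rule. SAP section 9 lists two changes from the protocol, and dropping the criterion is not one of them.

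**The concern.** The protocol's criterion still stands but is not assigned to a reference. If agreement reaches 65% against one tonometer and not the other, the plan gives no conclusion.

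A split result is foreseeable. Protocol 3.3 says GAT depends on corneal properties and DCT far less so. Section 4.9.1 reports that, with the related eyemate-IO device, differences from GAT grew with IOP. If GAT fell short and DCT did not, the statement in 8.2.2 that DCT is closer to true IOP would be a ready argument for preferring DCT afterwards, in an open-label study.

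The pair-count footnote adds freedom where it matters most. The conditional reference is the one more likely to fall short of 61 pairs, and the objective may then be adjusted without a stated rule.

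**Working it through.** **The plan's own figures.** Protocol 9.3 gives a significance level of 0.10 and power of 80%. These cannot be reproduced, because no expected agreement rate is stated and 9.2 says the sample size does not rest on a formal test. Read as an exact one-sided binomial test of 65%, they would need 45 of 61 pairs and a true rate of about 77.5%, or 86 of 120 pairs and about 75%. Neither rate is in the documents.

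**Inputs from the documents.** At most 24 patients (8.3.6) and five visits, V09 to V13. One averaged pair per eye and visit (SAP 8.5.1) gives at most 24 × 5 = 120 pairs per reference.

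**Assumed inputs.** True agreement within 5 mmHg of 60% for each reference, just below the bar. Thirteen eyes with DCT, so 13 × 5 = 65 pairs. The criterion is met when the observed proportion is at least 65%.

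**Step 1: independent pairs.** The count needed is k = 65% of n, rounded up, and P(meet) = P(X ≥ k) for X ~ Binomial(n, 0.60).
- n = 61, k = 40: 22.6%. Either of two independent references: 1 − (1 − 0.2255)² = 40.0%.
- GAT, n = 120, k = 78: 15.3%.
- DCT, n = 65, k = 43: 18.8%.
- Either of the last two, if independent: 1 − (1 − 0.153)(1 − 0.188) = 31.2%.

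**Step 2: clustering and correlation.** Pairs from one eye are not independent, and both differences use the same sensor in the same eye. I simulated normal differences with mean zero, scaled so that P(|d| ≤ 5) = 0.60, with 20,000 runs per setting. The between-eye share of variance ran from 0 to 0.7, and the correlation between the two references' differences from 0 to 0.9.

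| Between-eye share | GAT | DCT | At least one | Both |
|---|---|---|---|---|
| 0 | 15% | 19% | 28.5–31.3% | 3–6% |
| 0.3 | 17% | 20–21% | 30.5–34.5% | 4–7% |
| 0.5 | 20–21% | 23–24% | 34.6–39.6% | 5–10% |
| 0.7 | 24–25% | 28–29% | 39.6–45.7% | 7–13% |

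Ranges in the last two columns run over the correlation. A higher correlation lowers the chance for at least one and raises it for both.

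**Step 3: fewer DCT pairs.** With 65 possible pairs, five missed DCT visits leave 60, which is not more than 60. If a 65% bar were kept on fewer pairs, P(meet) on DCT at a true 60% would be 41.6% (20 pairs), 29.1% (30) or 31.7% (40), with pairs independent. Combined with 120 independent GAT pairs, at least one would meet it in 50.5%, 40.0% or 42.2%.

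**Step 4: can the SAP tables answer the criterion?** More than 60 pairs needs 61 / 5 = 12.2, so at least 13 eyes over all five visits. A single visit has at most 24 pairs. Mock-up Table 2.1.1 has columns V09 to V13 and no overall column, although SAP 8.6.2 does ask for the standard deviations overall. As planned, no table reaches more than 60 pairs.

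**The case against.** The strongest reply is that GAT already leads. The primary objective in the synopsis makes DCT conditional, protocol 6.2 says sensor pressure is compared with GAT, 8.2.2 names GAT as comparator, and SAP 8.5.1 lists only GAT and ARGOS-SC as primary outcome measures. This stands: the two references are not on equal terms. But it shows apparent intent, and none of these places ties the 65% to GAT.

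Four stronger readings are tempting, and the documents do not support them.
- *The plan allows success on either reference.* It states no such rule. GAT alone, either, or both are all left open.
- *GAT and DCT pairs may be pooled.* The SAP has separate tables (2.1.1 and 2.1.2) and separate figures (1–10 and 11–20), which makes this unlikely. They also mean that neither result can be quietly dropped. What stays open is the wording of the conclusion.
- *The type I error is inflated.* SAP 8.1.3 performs no tests, and nothing in the plan applies the 0.10 of protocol 9.3.
- *DCT exists only at some sites.* The documents say only that it is used when available, and Table 4 marks it at every visit. A selected DCT subset is a reasonable inference, not a stated fact.

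It is also fair that the size depends on the assumptions, and that 13 DCT eyes is the smallest number that can exceed 60 pairs. Choosing GAT is partly a judgement, since requiring both would also remove the ambiguity.

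**Conclusion.** The gap is real and should be closed: one criterion, two references, and no statement in either document of which decides. The consequence is a possible selective claim that the primary objective was met.

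The fair contrast is GAT alone against at least one reference. At a true agreement of 60% it is about 15% to 25% against about 28% to 46%, depending on clustering and correlation. The agreement rate, the DCT eye count, the clustering and the correlation are all assumptions, because the documents give none of them. Naming GAT removes the choice between references. It does not lower the 15% to 25% that comes from judging an observed proportion.

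A reader might also infer that rewording alone is enough. It is not, because the SAP's per-visit tables cannot address a criterion on more than 60 pairs.

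**What to change.** In the synopsis, protocol 8.1.3.1 and 9.1.4, and SAP 4.2.1 and 8.5.1, state that the 65% criterion is judged on ARGOS-SC versus GAT pairs only. GAT fits 8.2.2 and is scheduled at every visit. Report DCT agreement in the same format as supportive, without a pass or fail statement and not pooled with GAT.

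Add to the SAP one GAT table across V09 to V13 with the proportion of pairs within 5 mmHg. Any confidence interval on it should allow for several pairs per eye.

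The cost is one extra table and the wording changes. No new data are needed. The sponsor gives up the option of claiming success on DCT.

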### 8.1.3.2 Secondary endpoints

#### Safety

- Number of patients experiencing a device-related SAE (SADE) at any from V09 (month 12) throughout V13 (month 36).
- Incidence, nature, severity and seriousness of observed adverse events and adverse device events at any time from month 12 (V09) throughout month 36 (V13).

#### Performance

- Incidence, nature and seriousness of observed device malfunctions during from month 12 (V09) throughout month 36 (V13).

#### Utility

- User acceptance of the ARGOS-SC system at the investigational site by means of evaluation of physician acceptance questionnaires (by investigators)
- User acceptance of the ARGOS-SC system at home by means of evaluation of patient acceptance questionnaires (patients)
- Daily IOP self-measurement profiles (patients)

### 8.1.4 Equipment to be used to assess the clinical investigation variables and arrangements for monitoring maintenance and calibration

Sites will use their own diagnostic devices. The study monitor will verify that the sites maintain and calibrate these devices on a regular basis.

## 8.2 Investigational device(s) and comparator(s)

### 8.2.1 Description of the exposure to the investigational device(s) or comparators, if used

The ARGOS-SC pressure sensor is intended to be permanently implanted in the subject's suprachoroidal space concomitantly with a non-penetrating glaucoma surgery of the same eye. Subjects will be exposed to transient (2 seconds) low-levels of electromagnetic energy (0.25 W) emitted by the MESOGRAPH reading device during the reading sessions, at which time their skin may also be exposed to the MESOGRAPH outer surface.

 Implantdata Ophthalmic Products GmbH	Clinical Investigation Plan ARGOS-SC01_Follow-up	Revision C  Page 55 of 97
---	---	---------------------------------

IOP measurements will be made with the ARGOS-SC system at every follow-up visit. The values obtained at Visits 09 through Visit 13 will be compared to those obtained using GAT and if available Pascal DCT. Patients will also be requested to make daily measurements with the ARGOS-SC system in the out-patient setting.

### **8.2.2 Justification of the choice of comparator**

GAT, considered by the medical community to be the gold standard method of IOP measurement, will be used as comparator. However, GAT actually estimates IOP based on a measurement of the force needed to applanate a predetermined area of the cornea while the ARGOS-SC sensor will be in direct contact with the aqueous humor and measure IOP directly. Consequently, differences are anticipated between the IOP values obtained with the two devices. However, trends in IOP are expected to remain the same regardless of the method used. Therefore, to assess the accuracy of the ARGOS-SC system, IOP profiles obtained with ARGOS will be compared to those obtained with GAT.

Pascal DCT is designed to eliminate some of the measurement errors in GAT that come from variations in corneal thickness and rigidity. It is believed to be closer to true IOP, especially at higher IOPs. It is also less prone to “user error”.

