### **8.3.6      Number of subjects required**

This exploratory investigation will enroll maximal 24 patients.

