#### **9.3 Level of significance and the power of the clinical investigation**

Significance level is set to 0.10, Power to 80%.

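### Protocol 8.2.2 bases accuracy on comparing ARGOS-SC and GAT profiles, but the planned analyses show within-patient tracking only indirectly and SAP section 9 does not record the gap

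*Protocol*

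**What the plan says.** Protocol 8.2.2 gives a chain of reasoning. GAT estimates pressure through the cornea and the implant senses it directly, so their values may differ; nevertheless "trends in IOP are expected to remain the same regardless of the method used"; therefore, to assess accuracy, "IOP profiles obtained with ARGOS will be compared to those obtained with GAT". The word profile is not defined there. Protocol 8.2.1 fixes the paired occasions: "The values obtained at Visits 09 through Visit 13 will be compared to those obtained using GAT and if available Pascal DCT".

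The analysis sections take a different line:

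- Protocol 9.1.4 has one criterion, "accepted 65% of the measurements to agree between +/- 5 mmHg for > 60 measurement pairs".
- SAP 8.5.1 plans descriptive statistics per visit, a split of the absolute difference at 5 mmHg, Bland-Altman and scatter plots, and this: "The concordance of the intraindividual measurement values of GAT and ARGOS-SC will be indicated by the concordance correlation coefficient", calculated separately for each visit.
- Mock Table 2.1.1 sets the five visits in columns. Each of Figures 1 to 20 shows a single visit.
- SAP 8.6.2 has an overall summary, but only for the SD of the replicate readings, which is repeatability.
- SAP section 9 lists two changes from the protocol: home self-measurements were not recorded, and interim analyses were dropped. It does not mention the profile comparison.

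**The concern.** If levels may differ while trends should match, the natural evidence of accuracy is whether a patient's ARGOS-SC reading rises and falls with that patient's GAT reading. Nothing planned estimates this. SAP 8.5.1 calls its concordance intraindividual, but a coefficient calculated across patients at one visit depends heavily on how much patients differ from each other. The share within 5 mmHg needs only plausible levels.

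Protocol 4.1 presents the device as a way to detect peaks and trends between office visits, and this is the long-term performance study. Because self-measurements were not recorded, the clinic pairs at V09 to V13 are the only series left in which tracking against a reference method can be examined.

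The mean change in the difference from V09 does not fill the gap. If average pressure is stable, that mean is about zero for sensors that follow their patients and for sensors that do not.

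**Working it through.** The documents give no derivation for the 65% or for the figure of more than 60 pairs, so there is nothing to reproduce. With "This exploratory investigation will enroll maximal 24 patients" and five paired visits, at most 24 × 5 = 120 GAT pairs are available.

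**How lenient the criterion is.** For an unbiased normal difference with standard deviation SD, the share within 5 mmHg is 2Φ(5/SD) − 1. This equals 65% at SD = 5/z(0.825) = 5.35 mmHg. It is 90% at SD 3 and 79% at SD 4.

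**Inputs for a tracking check.** These are assumptions, in mmHg, and apply to visit averages: between-patient SD b = 3 to 4, visit-to-visit SD of true pressure v = 2 to 3, GAT error SD 1.5, sensor noise SD 1. A frozen sensor reads its patient's V09 level plus noise at every visit.

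| Quantity | Working sensor | Frozen at V09 level |
|---|---|---|
| SD of difference at V13 | √(1.5² + 1²) = 1.80 | √(2v² + 3.25) = 3.35 (v = 2), 4.61 (v = 3) |
| Share within 5 mmHg at V13 | 99.4% | 86.4%, 72.2% |
| Pooled share, V09 to V13 | 99.4% | (99.4 + 4 × 86.4)/5 = 89%; (99.4 + 4 × 72.2)/5 = 78% |
| r_ccc at V13 | 2(b² + v²)/[2(b² + v²) + 3.25]: 26/29.25 = 0.89 to 50/53.25 = 0.94 | 2b²/(2b² + 2v² + 3.25): 18/39.25 = 0.46 to 32/43.25 = 0.74 |
| Within-patient slope on GAT | v²/(v² + 2.25): 4/6.25 = 0.64 to 9/11.25 = 0.80 | 0 |

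Simulation of 24 patients and five visits, with 2,000 runs per combination, agrees:

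- Frozen sensors meet 65% in over 99% of runs.
- Mean r_ccc at V13 is 0.43 to 0.72 frozen and 0.88 to 0.93 working. These are slightly below the formula values because the sample is small.
- The SD of the difference at V13 is 3.3 to 4.6 frozen and 1.8 working.
- The 95% range of the within-patient slope is 0.51 to 0.77 for the weakest working case and within ±0.08 for frozen sensors.

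**A version closer to the documents.** Protocol 3.3 puts the imprecision of repeated IOP at ±5 mmHg. Read as a 95% range, this is a within-patient SD of 5/1.96 = 2.55. Protocol 4.7.1.4 gives a 3-sigma sensor accuracy of 2 mmHg, so SD 0.67. Assuming b = 4 and that 60% of the within-patient variance is true pressure change, frozen sensors keep 90% of pooled pairs within 5 mmHg. The repeated-measures correlation is 0.73 (95% of runs 0.63 to 0.82) for working sensors and 0.00 (−0.20 to 0.19) for frozen ones. If true change is only 30% of that variance, working sensors give 0.49 (0.33 to 0.63). With 13 patients and 60% true change, the ranges are 0.58 to 0.84 and −0.27 to 0.26.

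**What the per-visit outputs cannot separate.** Take b = 4, v = 2 and a sensor that follows its patient but whose noise SD has risen from 1 to 3. Its SD of the difference is √(2.25 + 9) = 3.35, the same as for the frozen sensor, and its r_ccc is 40/(40 + 11.25) = 0.78 against 0.74. The expected within-patient slope is 0.64 against 0.

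**The case against.** A reader might go further and infer that the primary analysis cannot tell a sensor that follows pressure from one that returns a fixed plausible value. The planned outputs do not support that.

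- One constant common to all patients would give r_ccc near 0 and a flat scatter plot.
- Sensors frozen at V09 would lower r_ccc, and the SD of the difference would rise from about 1.8 at V09 to 3.3 to 4.6 at V13. Mock Table 2.1.1 prints those columns side by side. A rise of at least 50% occurs in about 85 to 99% of frozen runs against 2 to 3% of working runs.
- A literally fixed reading would also show zero replicate SD under SAP 8.6.2.

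Three further arguments have weight. Section 8.2.2 justifies the comparator rather than specifying an analysis, and the formal primary objective is limits of agreement, which SAP 8.5.1 addresses. The SAP does not restate the 65% target and runs no test, so nothing in it is passed on that share alone. And no document suggests that sensors freeze; the long-term limit that Protocol 4.7.1.4 specifies is for drift, which would move the per-visit mean difference.

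All of this stands, and it limits the point without removing it. The signals are indirect, carry no stated threshold and are not specific to tracking. None shows which patient is affected. The comparison that 8.2.2 names is still neither planned nor recorded as dropped.

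**Conclusion.** The gap between Protocol 8.2.2 and the analyses in Protocol 9.1.4 and SAP 8.5.1 is real and comes from the text alone. It starts in the protocol, whose own analysis section has no profile comparison. The 65% criterion does not test tracking: under the assumed SDs, frozen sensors meet it in over 99% of runs with 78 to 89% of pooled pairs inside the limit. The other planned outputs would change visibly, so the point is lack of a direct and specific measure, not blindness.

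The size depends on assumptions. If the frozen value is one V09 reading with the same within-patient SD as GAT, the visits after V09 fall below 65% once that SD exceeds 5.35/√2 = 3.8 mmHg (62% at SD 4). The frozen sensor is an illustration, not a predicted failure. This is an inexpensive improvement to a descriptive study; it does not invalidate the primary analysis.

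**What to change.** In SAP 8.5.1:

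- Define profile as each patient's paired ARGOS-SC and GAT series over V09 to V13.
- Regress ARGOS-SC on GAT with patient as a factor, and report the slope and the repeated-measures correlation, each with a two-sided 95% CI. The slope is needed as well because the correlation is undefined if readings do not vary at all.
- Plot both series for each patient.
- Do the same for DCT where it is available.
- State that GAT error pulls the slope below 1 even for a working sensor (0.64 to 0.80 under the assumptions above), so 1 is not the benchmark, and that the analysis is descriptive and supports the limits of agreement.

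If the sponsor prefers not to add this, SAP section 9 should record that the comparison in Protocol 8.2.2 is not performed, with the reason.

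The cost is a paragraph of SAP text, one table block and one figure set. No new data are needed.
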